#### 10.9.3.3. Adjustment for covariates

The risk for malaria infection and development of clinical disease depends on numerous factors related to the parasite, host and vector biology. Estimates of the vaccine efficacy will be made, firstly based on treatment group and secondly adjusted for:

- age: continuous variable.
- geographical area ('barrios' local government areas): categorical variable.
- distance from health center (in kilometers): continuous variable.

An exploratory examination of the marginal effect each of the above covariates have on the treatment estimate may also be undertaken.

#### 10.9.4. Exploratory analysis

The exploratory endpoints will be analyzed in the Total Vaccinated Cohort and the ATP Cohort for efficacy.

For the first exploratory endpoint (time to the first clinical episode of symptomatic *P*. *falciparum* malaria defined as the presence of *P*. *falciparum* asexual parasitemia above 500 per  $\mu$ L on Giemsa stained thick blood films AND the presence of fever [axillary temperature  $\geq 37.5^{\circ}$ C] at the time of presentation), the time at risk is defined as in Section 10.9.3.1. However, the time at risk will begin at Day 0 and no adjustments will be made for the absences from the study area and the anti-malarial drug therapy. Vaccine efficacy will be calculated in the same manner as described in Section 10.9.3.2 using Cox regression models. Only crude estimates, not adjusted for prognostic/stratifying factors will be presented.

This analysis will be done including cases from the passive case detection only (see Section 5.1.16) and including cases from both the passive case detection and the active detection of infection (ADI, see Section 5.1.17)

Note that the total number of clinical episodes will only be analyzed at the end of the single-blind phase.

The frequency of CS-specific CD4+ and CD8+ T cells will be summarized for each group at each timepoint (descriptive statistics).

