#### 1.3.3.3.7. Efficacy analysis in the ITT Cohort from Day 0, Malaria-026

For safety reasons, the FDA requested the analyses from Day 0 be conducted on the Primary Case Definition in the ITT Cohort. This was repeated for all clinical attacks fitting the Primary Case Definition and the incidence of anemia. For the analysis of the ITT Cohort the time at risk was not adjusted for temporary travel from the study area, malaria drug usage or for previous clinical episodes, and no adjustment was made for covariates.

The VE for the Primary Case Definition was 30.2% (95% CI 14.4% to 43.0%; p < 0.001). The estimate of VE against all clinical episodes was 33.5% (95% CI 16.4% to 47.1%; p < 0.001). The estimate for VE against incidence of anemia was 24.8% (95% CI -12.8% to 49.9%; p=0.168). The estimate for VE for severe malaria disease was 48.5% (95% CI 7.3% to 73.1%; p=0.027); for hospitalized malaria the VE was estimated to be 31.2% (95% CI 3.1% to 51.5%; p=0.032).

The results in the ITT Cohort from Day 0 were consistent with the results of the ATP Cohort for Efficacy post Dose 3 for all the endpoints analyzed

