The process for each vaccination is as follows. The identity of the child will be confirmed using the study identification card. The subject number on this card will be cross-checked with that on the subject's clinic form, ensuring that the subject number on the clinic form matches that of the study identification card. On the day of the first vaccination the inclusion/exclusion criteria and consent form will be checked prior to vaccination. On the days of the subsequent vaccinations, elimination criteria and contraindications to vaccination will be checked prior to vaccination. A vaccine clinic form will be initiated, which will give the child's identifiers, subject number and treatment number assigned after the administration of the vaccine.

For each vaccination during the course of the study, the Vaccinator will prepare and administer the vaccine for a specific subject. Since the vaccines used in this study are of distinct appearance, the Vaccinators are not blinded and perform no other function in the study (refer to Section 6.5). The Vaccinator will select the sealed box labeled with the subject's treatment number, containing the vials numbered with the treatment number, remove the vaccine vials and fill a syringe according to this study protocol (refer to Section 6.2). The Vaccinator will then place a numbered opaque label with the subject's treatment number on the syringe. The purpose of masking the syringe is to blind the parent(s) or guardians(s) of the subject. After administering the vaccination to the subject the Vaccinator will enter the treatment number administered to the subject on the clinic form.

Subjects who cannot be vaccinated on the originally scheduled date (due to an acute illness on the judgment of the PI or designate, local lesion at the injection site or scheduling conflicts) will be vaccinated within 7 days and undergo all study procedures

for the visit on the same day as vaccination. In the particular case of any child found to be febrile (axillary temperature  $\geq 37.5^{\circ}$ C), a blood slide will be taken to investigate for malaria. Children will be treated as appropriate for their condition and will be followed up until resolution of any symptoms and be vaccinated if their clinical symptoms resolve within 7 days.

Those who cannot be re-vaccinated within 7 days of their scheduled date will continue all study procedures apart from receiving further study vaccinations.

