#### (Amended 12 April 2005)

#### Clinic Visit 2: Dose 1 of TETRActHib Day 0

- Check study identification card of vaccinee
- Check inclusion/exclusion criteria
- Take medical history and carry out physical examination
- Measure body weight
- Check contraindications to vaccination
- Record pre-vaccination body temperature
- Randomize subjects
- Administer the first dose of TETRActHib intramuscularly in the right thigh

Each infant will be assessed for at least 60 minutes after vaccination to evaluate and treat any acute adverse events.

- Record any post-vaccination solicited symptoms
- Record any post-vaccination unsolicited adverse events
- Record any post-vaccination SAEs
- Record concomitant medication

#### Field worker post vaccination follow up visits 21 to 26 Days 1, 2, 3, 4, 5 and 6

- Record axillary temperature of subject
- Record local (pain and swelling at the injection site) and general (fever, irritability / fussiness, drowsiness, loss of appetite) solicited adverse events
- Record SAEs experienced by the vaccinee since the last visit
- Record unsolicited adverse events experienced by the vaccinee since the last visit
- Record concomitant medication

#### Clinic Visit 3: Dose 1 of RTS,S/AS02D or Engerix-B Day 14

- Check study identification card of vaccinee
- Carry out physical examination
- Record SAEs experienced by the vaccinee since the last visit
- Record any unsolicited adverse events since the previous vaccination
- Check contraindications to vaccination
- Check elimination criteria
- Record pre-vaccination body temperature
- Administer the first dose of RTS,S/AS02D or Engerix-B intramuscularly in the left thigh

Each infant will be assessed for at least 60 minutes after vaccination to evaluate and treat any acute adverse events.

- Record any post-vaccination solicited symptoms
- Record any post-vaccination unsolicited adverse events
- Record any post-vaccination SAEs
- Record concomitant medication

#### Field worker post vaccination follow up visits 27 to 31 Days 15, 16, 17, 18 and 19

- Record axillary temperature of subject
- Record local (pain and swelling at the injection site) and general (fever, irritability / fussiness, drowsiness, loss of appetite) solicited adverse events
- Record SAEs experienced by the vaccinee since the last visit
- Record unsolicited adverse events experienced by the vaccinee since the last visit
- Record concomitant medication

#### Clinic Visit 4: Collection of blood sample Day 20

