#### 10.6.4. According to protocol (ATP) cohort for analysis of efficacy

The ATP cohort for analysis of efficacy will include all evaluable subjects (i.e. those meeting all eligibility criteria, complying with the procedures defined in the protocol, with no elimination criteria during the study) for whom data concerning efficacy endpoint measures are available.

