# 10.9.3. Analyses of efficacy

#### 10.9.3.1. Calculation of the time at risk

For the efficacy endpoint (time to first malaria infection), the time at risk will be counted in days, and expressed as child years at risk (days/365.25).

For each subject in the Total Cohort, time at risk begins 14 days after Dose 3 for those that received Dose 3 or 2/2 months after Dose 1 (Day 75 90) otherwise. For the According to Protocol cohort, time at risk begins 14 days after Dose 3 (Amended 12 April 2005).

The time at risk will end whenever one of the following conditions happen first: fits the case definition for malaria infection, loss of follow up, emigration from the study area, withdrawal, death, end of follow-up period (Clinic Visit 11).

The time at risk will take into account absences from the study area and anti-malaria drug therapy. The monthly home visits will be used to determine any period of travel outside the study area. Absences from the study area of 2 weeks or more will be recorded in multiples of 1 week. The date of departure will be documented. Similarly, if treatment for malaria is administered, the subject will not be considered susceptible to malaria infection for the longest duration of the combination of drugs the subject could receive for this episode as follows: 28 days if received sulphadoxine-pyrimethamine, 7 days if having received chloroquine alone, 7 days if having received co-artemesinin.

If an episode is detected during a period of time not counting for the time at risk it will not be included in the analysis, however a table will be presented showing the number of such episodes not included in the analysis.

Episodes will be included in the analysis only if the child is identified properly showing his/her ID Card at the contact with the health facility and the study number is written in the OPD form. Only blood slides that complete the reading process according to SOP will be considered in the establishment of a malaria infection.

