### 10.10.3. Analyses of efficacy

#### 10.10.3.1. Exploratory analysis

The exploratory endpoints will be analyzed in the Total Vaccinated Cohort and the ATP Cohort for efficacy.

For the first exploratory endpoint (time to the first clinical episode of symptomatic *P*. *falciparum* malaria defined as the presence of *P*. *falciparum* asexual parasitemia above 500 per  $\mu$ L on Giemsa stained thick blood films AND the presence of fever [axillary temperature  $\geq 37.5^{\circ}$ C] at the time of presentation), the time at risk is defined as in Section 10.9.3.1. However, the time at risk will begin at Day 0 and will end whenever one of the following conditions happen first: fits the case definition for malaria infection, loss of follow up, emigration from the study area, withdrawal, death, end of follow-up period (Clinic Visit 12, end of single blind phase). The time at risk will not be adjusted for the absences from the study area and the anti-malarial drug therapy. Vaccine efficacy will be calculated in the same manner as described in Section 10.9.3.2 using Cox regression models. Only crude estimates, not adjusted for prognostic/stratifying factors will be presented.

For the analysis of the total number of clinical episodes, the incidence of episodes (total number of episodes/person years at risk) for each group will be presented. The significance of the group effect will be assessed using Poisson regression models with random effects including the time at risk as an off-set variable. Vaccine efficacy is defined as 1-R where R is the rate ratio of clinical episodes of the RTS,S/AS02D group versus the Engerix-B group (with 95% CI). Only crude estimates, not adjusted for prognostic/stratifying factors will be presented.

Both analyses will be done including cases from the passive case detection only (see Section 5.1.16).

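### Clinical malaria in the ATP efficacy cohort is timed from Day 0, although membership of that cohort is decided by compliance after Day 0

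*Protocol*

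**What the plan says.** Section 10.9.4 of the protocol sets the cohorts for the clinical-malaria endpoints: "The exploratory endpoints will be analyzed in the Total Vaccinated Cohort and the ATP Cohort for efficacy". It takes the time-at-risk definition from Section 10.9.3.1 and then changes the start: "However, the time at risk will begin at Day 0 and no adjustments will be made for the absences from the study area and the". That sentence closes by naming antimalarial treatment as the other thing left unadjusted. Section 10.10.3.1 repeats this for the annex analysis, with the same two cohorts: "However, the time at risk will begin at Day 0 and will end whenever one of the following conditions happen first". Section 10.4 also counts these endpoints from Day 0 and names no cohort.

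The visit schedule in Section 5.4 defines the origin: "Clinic Visit 2: Dose 1 of TETRActHib Day 0". The randomised vaccine (RTS,S/AS02D or Engerix-B) is given on Days 14, 44 and 74.

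For the infection endpoint, Section 10.9.3.1 uses a different ATP start: "For the According to Protocol cohort, time at risk begins 14 days after Dose 3".

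Section 10.6.4 limits the ATP efficacy cohort to evaluable children, including those "complying with the procedures defined in the protocol, with no elimination criteria during the study". Section 5.3 adds that the intervals between visits determine evaluability for the ATP analyses.

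**The concern.** A Day 0 clock suits a cohort whose membership is settled by Day 0. ATP membership is not: it is known only once the child has kept to the vaccination schedule, which runs to Dose 3. Time before that point is counted only for children who later qualified.

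The endpoint itself can cause the exclusion. The case definition requires an axillary temperature of at least 37.5°C. Section 4.6 makes the same temperature a reason to postpone vaccination, and Section 5.1.11 states: "Those who cannot be re-vaccinated within 7 days of their scheduled date will continue all study procedures apart from receiving further study vaccinations". An early malaria episode can therefore stop the course and take the child out of the ATP cohort. The event goes too, although the period in which it occurred is still analysed.

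At stake is what the ATP figure means. It mixes time before vaccination, time part-way through the course and time after the full course, in a selected group. It could not properly be set beside this trial's ATP estimate against infection, or beside the Malaria-026 ATP estimate, both of which start 14 days post Dose 3.

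**Working it through.** **1. Risk-time shares (Section 5.4 calendar)**
- Before any randomised vaccine: 14/180 = 7.8% of follow-up to Clinic Visit 11 (Day 180).
- Before 14 days post Dose 3: 74 + 14 = 88 days, and 88/180 = 48.9%. The nominal date of Clinic Visit 9, Day 90, gives 50%.
- Annex to Month 14: 14 × 30.4 ≈ 426 days, and 88/426 = 20.7%.

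**2. How membership depends on later events**
- Section 10.6.4 requires compliance and no elimination criteria during the study.
- Section 5.3 ties evaluability to visit intervals.
- Section 10.9.3.1 gives the Total Cohort a fallback start for children without Dose 3 and gives the ATP cohort none. This implies that ATP children have received Dose 3, although Section 10.6.4 does not list three doses.

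**3. The precedent**

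In Malaria-026 the Day 0 start went with the ITT cohort (Section 1.3.3.3.7): "For safety reasons, the FDA requested the analyses from Day 0 be conducted on the Primary Case Definition in the ITT Cohort". That analysis also made no adjustment for travel, antimalarial use or covariates. The ATP analysis started 14 days post Dose 3 (Section 1.3.3.3.1). Section 10.9.4 carries the ITT features over to both cohorts.

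**4. Illustrative size**

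The protocol gives no sizing for the clinical endpoint, so there is no stated figure to reproduce. From the document: 30% efficacy against a first clinical episode (Section 1.4.2), taken here as the effect from Day 88. Assumed: 30% control attack rate by Day 180; hazard before Day 88 equal to 0.25, 0.5 or 1 times the later hazard; no effect on Days 0–14; no early cases removed. The limiting Cox hazard ratio was solved from the partial-likelihood score with these piecewise hazards.

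| Efficacy, Days 14–88 | Estimate at Day 180 (early hazard 1 to 0.25) | Estimate at Month 14 |
|---|---|---|
| 0% | 14% to 24% | 22% to 27% |
| 15% | 21% to 26% | 25% to 28% |
| 30% | 27% to 29% | 29% to 30% |

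The first row can be checked by hand. With no early effect, log HR ≈ (1 − w) × ln 0.70, where w is the share of first cases before Day 88.
- Equal hazard, w = 0.57: 0.43 × (−0.357) = −0.153, HR 0.858, estimate 14%.
- Early hazard 0.25, w = 0.25: 0.75 × (−0.357) = −0.268, HR 0.765, estimate 23.5%.

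A variant assumes no effect before Day 28, a hazard cut to 10% on Days 60–88 after the presumptive antimalarial, and Month 6 attack rates of 20% to 50%. It gives 16% to 25% with no early effect and 20% to 27% with half effect. Together the two models span about 14% to 27%.

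**5. What changes the answer**
- Attack rate: in the equal-hazard, no-effect case, 10% to 70% moves the estimate from 15% to 11%.
- Early cases leaving the ATP cohort: with no early effect, removing half gives 19% to 26%. Removing all gives 30%, with no dilution.
- Early efficacy above later efficacy (60% then 30%): the estimate is 34% to 40%, away from zero.

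**The case against.** A reader might infer three stronger things, and the documents support none of them.

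*That Section 10.9.4 contradicts Section 10.9.3.1.* It does not. It cites that section and then states a different start, and Section 10.4 defines these endpoints from Day 0. This is a declared departure for a different endpoint.

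*That the estimate must be pulled towards zero.* The Malaria-026 figures do not show this. Efficacy was 30.2% from Day 0 (ITT) against 26.9% crude and 29.9% adjusted from 14 days post Dose 3 (ATP). For all episodes it was 33.5% against 27.3%. Severe malaria went the other way, 48.5% against 57.7%. Cohorts and adjustment differ, so these comparisons are only indicative. Dropping early cases also offsets dilution. The illustration models dilution alone, which a Day 0 analysis in the Total Vaccinated Cohort would share.

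*That all 88 days are pre-vaccination time.* Only Days 0–14 are. Days 14–88 are partly vaccinated.

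Other objections carry weight. The endpoints are exploratory, and the legitimate Day 0 analysis in the Total Vaccinated Cohort is already planned. Equal early hazard, the worst case, sits badly with Section 1.4, which places severe malaria from about 4 months of age. Precision is low: with 100 per group and a 30% control attack rate there would be about 30 + 22 = 52 first cases, and with SE ≈ 2/√52 = 0.277 a 30% efficacy has a 95% CI of about −20% to 59%.

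The non-proportionality checks in Section 10.9.3.2 do not answer the point. They can describe an effect that builds over time, but the piecewise periods are cut by event counts rather than at Day 88, and no such model undoes selection into the cohort.

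**Conclusion.** The point stands in a limited form. From Day 0, the ATP clinical-malaria analyses count follow-up that is conditioned on later compliance: 49% of the first 180 days, and about 21% of the annex period, precede 14 days post Dose 3. The resulting estimate describes neither all vaccinated children nor a completed course.

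Dilution is probable if protection builds with doses. On the assumptions above, with no or half effect early and no early cases removed, a true 30% would appear as roughly 14% to 27% at Month 6. The early hazard, the clinical attack rate, the early efficacy and the share of early cases lost from the ATP cohort are all assumed, and other plausible values give no bias or an upward one. An uncertain sign makes the ATP figure harder to interpret. The primary safety endpoint, the infection endpoint and its sample size are unaffected.

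**What to change.** In Sections 10.9.4 and 10.10.3.1, keep the Day 0 start for the Total Vaccinated Cohort only. For the ATP efficacy cohort, start time at risk 14 days after Dose 3, as Section 10.9.3.1 already does for infection, or drop the Day 0 ATP version. Align Section 10.4 so that it gives the start time by cohort.

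The cost is a wording change in three sections and reuse of an existing derivation, with no new data and no change in sample size. The ATP analysis loses its early events, which stay in the Total Vaccinated Cohort analysis. Some conditioning remains after the change, because ATP membership still requires that no elimination criterion applies during the study. The ATP result should be described accordingly.

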# 10.10. Annex analysis at study conclusion

# 10.10.1. Analyses of safety

The analysis of the occurrence of SAEs will be performed on the Total Vaccinated Cohort. The proportion of subjects with an SAE, classified by the MedDRA preferred term level, reported from study start until study conclusion (end of the single-blind phase) will be tabulated with exact 95% CI. Comparisons between groups will be done using Fisher's Exact test for each preferred term.

Serious adverse events and withdrawal due to adverse event(s) will be described in detail.

Biochemistry (ALT, bilirubin, creatinine) and hematology (hemoglobin, WBC, platelets) values that are outside of the reference ranges will be described for Clinic Visit 12 (end of single-blind phase).

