- At each contact for ADI, history of fever will be recorded and axillary temperature taken; a blood sample will be taken for malaria parasite genotyping and a smear will be taken for detection of malaria parasites.
- Subjects who are symptomatic at the time of ADI contact (i.e. history of fever within previous 24 hours or axillary temperature >37.5°C) will have a blood slide read and treated within the same day if the blood slide is positive.
- Infants will be followed passively for the occurrence of clinical malaria for the duration of their participation in the study. Cases will be detected at all health facilities in the study area.
- Infection with malaria parasites is defined as *P. falciparum* as exual parasitemia > 0
- Data collection will be by conventional CRF.
- Duration of the study will be 14 months per subject.
- The final analysis of the study for all primary and secondary endpoints will take place on all data collected up to the end of the surveillance for ADI (Clinic Visit 11)
- All children will be followed for safety for a period that extends to 12 months post Dose 3. All data collected after the Final Analysis (Clinic Visit 11) will be reported in an Annex Report.
- This study is overseen by a formally constituted DSMB operating under a charter. During the vaccination phase of the study full safety reports will be sent to the DSMB at 3 points corresponding to; after 30, 60 and 100 subjects have been enrolled and have completed the first 7 days of follow-up post Dose 1 of RTS,S/AS02D or Engerix-B.

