# 9. SUBJECT COMPLETION AND WITHDRAWAL

# 9.1. Subject completion

A subject who returns for the concluding visit/is available for the concluding contact foreseen in the protocol is considered to have completed the study.

A subject that comes for Clinic Visit 11 has completed the double-blind phase of the study. A subject that comes for Clinic Visit 12 has completed the single-blind phase of the study.

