# 10. DATA EVALUATION: CRITERIA FOR EVALUATION OF OBJECTIVES

#### 10.1. Primary Endpoints

#### 10.1.1. Primary endpoint; safety

• Occurrence of SAEs from the time of first TETRActHib vaccination until months 6 post Dose 1

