# **10.3.** Tertiary Endpoints

#### 10.3.1. Tertiary endpoints for Safety

• Occurrence of serious adverse events during the single-blind surveillance period (from Month 7 to Month 14 inclusive).

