#### 10.5.1. Safety

This is the first administration of RTS,S/AS02D to infants and therefore the sample size of this Phase 1/2 safety study is limited to 200. Therefore only large differences in the frequencies of SAEs can be detected with reasonable power. The data set will be examined, comparing the rates of SAEs at the Medical Dictionary for Regulatory Activities (MedDRA) preferred term level. A sample size of 200 has the power to detect differences in the rates of safety endpoints (SAEs at the MedDRA preferred term level) as shown in Table 26. All calculations were performed with PASS 2000, using an asymptotic test for difference in proportions, type I error rate of 5% and no correction for multiplicity.

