# 10.9.1. Analyses of safety

#### 10.9.1.1. Primary endpoint

For the safety primary endpoint, the occurrence of SAEs will be performed on the Total Vaccinated Cohort. The proportion of subjects with an SAE, classified by the MedDRA preferred term level, reported from study start until study conclusion (end of the doubleblind phase) will be tabulated with exact 95% CI. Comparisons between groups will be done using Fisher's Exact test for each preferred term. If the percent of enrolled subjects excluded from the ATP cohort for analysis of safety is more than 5%, a second analysis based on this ATP cohort will be performed to complement the Total Analysis.

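### The tertiary safety endpoint is SAEs in Months 7 to 14, but the annex analysis tabulates and tests SAEs only from study start, so no planned table or test estimates the endpoint

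*Protocol*

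**What the plan says.** Section 10.3.1, and the synopsis in the same terms, gives the tertiary safety endpoint as "Occurrence of serious adverse events during the single-blind surveillance period (from Month 7 to Month 14 inclusive".

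Section 10.10.1 is the SAE analysis at study conclusion. It uses the Total Vaccinated Cohort and takes the proportion of subjects with an SAE by MedDRA preferred term, "reported from study start until study conclusion (end of the single-blind phase) will be tabulated with exact 95% CI". On testing it says: "Comparisons between groups will be done using Fisher's Exact test for each preferred term". It adds that SAEs and withdrawals due to adverse events will be described in detail.

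The first part of that window already has its own endpoint and analysis. The primary endpoint (Section 10.1.1) is "Occurrence of SAEs from the time of first TETRActHib vaccination until months 6 post Dose 1". Its analysis (Section 10.9.1.1) takes SAEs "reported from study start until study conclusion (end of the doubleblind phase) will be tabulated with exact 95% CI". Section 9.1 fixes the boundary: "A subject that comes for Clinic Visit 11 has completed the double-blind phase of the study". The design overview (Section 3) says of the later data: "All data collected after the Final Analysis (Clinic Visit 11) will be reported in an Annex Report".

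**The concern.** The endpoint and the analysis cover different periods. The endpoint is what happens in Months 7 to 14. The analysis is the cumulative proportion from study start to Month 14, which counts again every subject already in the primary analysis. An analyst who followed Section 10.10.1 to the letter would never report the quantity in Section 10.3.1.

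This is more than detail left to an analysis plan, because the protocol fixes a window and that window conflicts with its own endpoint. The other tertiary endpoints do match: anti-HBs and anti-CS at 12 months post Dose 3 (Section 10.3.2) are analysed at Clinic Visit 12 (Sections 10.10.2.1 and 10.10.2.2).

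At stake is whether a between-group difference that arises only after Month 6 can be read from the annex report, or whether it appears only mixed with what happened earlier.

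**Working it through.** **1. Windows side by side**

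- Primary endpoint and its analysis: study start to Clinic Visit 11 (Month 6).
- Tertiary endpoint: Months 7 to 14.
- Annex SAE analysis: study start to Month 14.

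No section gives a table, confidence interval or test limited to Months 7 to 14.

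**2. Can the endpoint be recovered by subtraction?** For one preferred term in one arm, let A be the subjects in the annex table, B the subjects in the final-analysis table and D the subjects with that term in both periods. Each subject counts once per term, so A − B is the number whose first event of that term fell after the double-blind phase. The endpoint count is A − B + D. Neither table shows D, so subtraction gives only a lower bound.

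**3. Effect on a comparison.** The protocol states no figure for this endpoint. Its SAE power table (Table 26) uses 100 per group, with "type I error rate of 5% and no correction for multiplicity". The calculation here keeps 100 per arm and 5%, takes the test as two-sided (an assumption) and enumerates Fisher's exact test. On Table 26's own pairs (1/12, 3/15, 5/19 and 10/26%), Fisher power is 89, 82, 84 and 81%, against the stated 80% from an asymptotic test. The setting is therefore comparable.

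With early risk e and late risk l, independent between periods (an assumption), the cumulative risk is 1 − (1 − e)(1 − l). Take late risks of 10% v 25% and the same early risk in both arms:

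| Early risk | Cumulative risks | Difference (points) | Fisher power |
|---|---|---|---|
| none (defined window) | 10.0% v 25.0% | 15.0 | 76% |
| 1% | 10.9% v 25.75% | 14.85 | 73% |
| 5% | 14.5% v 28.75% | 14.25 | 63% |
| 10% | 19.0% v 32.5% | 13.5 | 53% |
| 20% | 28.0% v 40.0% | 12.0 | 37% |

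For example, at 10% early risk: 1 − 0.90 × 0.90 = 0.190 and 1 − 0.90 × 0.75 = 0.325.

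**4. Unequal early risk** (control v vaccine)

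- Same direction: early 5% v 10%, then late 10% v 25%. Cumulative 1 − 0.95 × 0.90 = 14.5% v 1 − 0.90 × 0.75 = 32.5%. Power is 82%, above the 76% on the defined window.
- Opposite direction: early 20% v 10%, then late 5% v 19%. Cumulative 1 − 0.80 × 0.95 = 24.0% v 1 − 0.90 × 0.81 = 27.1%. Power is about 6%, against 84% on the defined window.

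The early risks are assumptions, since the protocol gives no infant SAE rate by preferred term. Its nearest guide to a common term is the earlier trial in Mozambican children aged 1 to 4 years (Malaria-026). There, SAE reports of malaria in those under 24 months in Cohort 1 were 19% with vaccine v 33% with control.

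**The case against.** The case against giving this weight is fair in most respects.

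- **Late SAEs are not lost.** Section 10.10.1 describes SAEs in detail and Section 3 sends post-Visit 11 data to the Annex Report. A reader might infer that late events go unreported, but the documents do not support that. What is missing is the between-group table for the defined window. The report and analysis plan foreseen in Section 6.5 could add it, which softens the mismatch but leaves the protocol text wrong.
- **No hypothesis is attached.** The safety objective is to describe, and Section 10.5.1 says only large differences are detectable. Loss of power is a weak measure of harm for a descriptive tertiary table. This stands, and it lowers the severity.
- **Dilution is conditional.** A reader might infer that the cumulative table always shrinks a late difference. Step 4 shows that it can also enlarge one.
- **The loss is small for most terms.** A reader might set it from the share of children with any SAE in Malaria-026 (14% to 37% by age and arm in Cohort 1). That does not carry over: the planned test is per preferred term, and those children were older. At a per-term early risk of 1% the loss is about 3 points.
- **Waning malaria protection is partly covered elsewhere.** Section 10.10.3.1 analyses first clinical malaria to Clinic Visit 12 by the methods of Section 10.9.3.2, which provide for non-proportional hazards. That stands for clinical malaria, but not for SAEs in general.
- **A late-window comparison has its own weakness.** Limiting it to children still followed at Month 7 conditions on events after randomisation. That is a reason to keep the cumulative Total Vaccinated Cohort table.

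**Conclusion.** The mismatch is real and needs no assumption: the endpoint is Months 7 to 14, the only planned SAE table and test run from study start to Month 14, and the first cannot be derived from the planned tables.

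The size depends on assumption. With 100 per arm, two-sided Fisher at 5%, independent periods and equal early risk, power for a late 10% v 25% difference falls from 76% by about 3 points at an early per-term risk of 1%, but by about 39 points at 20% (76% to 37%). It is material only for common terms, of which malaria is the obvious candidate. If early risks differ between arms, the direction of the distortion depends on theirs.

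Severity is minor. The endpoint is tertiary and descriptive, and the primary safety analysis and the sample size are unaffected.

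**What to change.** In Section 10.10.1, add for the tertiary endpoint the proportion of subjects with an SAE with onset in Months 7 to 14, by preferred term, with exact 95% CI and Fisher's exact test. Use the Total Vaccinated Cohort and either show the number still in follow-up at the start of the window or use that number as the denominator, saying which. State when the window opens; Section 5.1.14.2 treats the single-blind phase as beginning after Clinic Visit 11. Keep the study-start-to-Month 14 table alongside it.

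The cost is one extra table and a wording change. SAEs are already collected monthly to Month 13 and at Clinic Visit 12. The price in interpretation is that the late comparison is not strictly of the full randomised set, which the report should say.
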